### **Statement of Compliance to protocol, GCP and applicable regulatory guidelines:**

This trial will be conducted in compliance with the protocol, ISO 14155:2020, the International Council for Harmonization Good Clinical Practice E6(R2) (ICH GCP), the Declaration of Helsinki, and all applicable regulatory requirements.

**MEDICAL MONITOR**

The Medical Monitor must be notified by the clinical institution/site by e-mail or telephone within 24 hours of learning of a Serious Adverse Event. The Medical Monitor may be contacted during business hours for adverse event questions. General study related questions should be directed towards your assigned clinical research associate.

The Medical Monitoring Plan is maintained as a separate document and included in the Trial Master File.

**Clinical Study Protocol**  
**Johnson & Johnson Vision Care, Inc.**

**CHANGE HISTORY**

Version	Originator	Description of Change(s) and Section Number(s) Affected	Justification for Change	Date
1.0	[REDACTED]	New Protocol	NA	07 Sep 2021
2.0	[REDACTED]	Update Section 7.2, Step 1.8: remove GSI Background questionnaire	Questionnaire is not being used	14 Sep 2021

# Clinical Study Protocol

## Johnson & Johnson Vision Care, Inc.

### SYNOPSIS

Protocol Title	Validation of senofilcon A with new UV / HEV Filter
Sponsor	JJVC, [name]
Clinical Phase	Clinical trial phase: confirmatory Design control phase: Confirmatory phase, phase 3
Trial Registration	This study will be registered on ClinicalTrials.gov by the Sponsor
Test Article(s)	Investigational Products: senofilcon A with new UV / HEV filter Approved Products: senofilcon A without new UV / HEV filter (ACUVUE OASYS 1-Day)
Wear and Replacement Schedules	Wear Schedule: daily wear Replacement Schedule: daily disposable
Objectives	This study is being conducted to validate that the Test lens meets the customer requirements. Primary Objectives: The Test lens will meet the safety and efficacy requirements of the Design Validation Requirements. Secondary Objectives: The Test lens will meet the Market Preference Requirements.
Study Endpoints	Primary endpoint(s): logMAR acuity, biomicroscopy, fit acceptance, CLUE vision Secondary endpoint(s): CLUE handling, CLUE comfort, situational visual performance – digital devices, and situational visual performance - indoors
Study Design	This is a bilateral, dispensing, randomized, controlled, subject-masked, 2-arm parallel study. Each subject will be bilaterally fitted with one of the two study articles during the course of the study. There will be a total of 2 visits: 1. Visit 1: Screening, baseline evaluation and lens fit #1 2. Visit 2: Follow-up to lens fit #1. Final evaluation See the flow chart at the end of the synopsis table for the schematic of the study visits and procedures of main observations (Figure 1).

**Clinical Study Protocol**  
**Johnson & Johnson Vision Care, Inc.**

Sample Size	Approximately 320 subjects in total (enrolling ~160 in the Test lens group and 160 in the Control lens group with the aim to complete approximately 286 subjects (~143 in each of the 2 lens groups).
Study Duration	Subject enrollment will last 4 weeks per site. Once enrolled, subjects will be in the study for approximately 2 weeks, making the entire study approximately 6 weeks in duration.
Anticipated Study Population	Subjects will be male and female of any race and ethnicity, age 18 through 39, habitual wearers of spherical silicone hydrogel contact lenses within the power range of -1.00 through -6.00 D. Subjects will be targeted in a 7:3 ratio based on habitual lens wear (7 habitual daily disposable wearers versus 3 habitual daily wear reusable wearers) within each lens group.

# Clinical Study Protocol

## Johnson & Johnson Vision Care, Inc.

Eligibility Criteria - Inclusion	
Potential subjects must satisfy all of the following criteria to be enrolled in the study:
 
Inclusion Criteria after Screening
 
The subject must:
 

1. Read, understand, and sign the STATEMENT OF INFORMED CONSENT and receive a fully executed copy of the form.

2. Appear able and willing to adhere to the instructions set forth in this clinical protocol.

3. Be between 18 and 39 (inclusive) years of age at the time of screening.

4. By self-report, habitually wear spherical silicone hydrogel soft contact lenses in both eyes in a daily reusable or daily disposable wear modality (i.e. not extended wear modality). Habitual wear is defined as a minimum of 6 hours of wear per day, for a minimum of 5 days per week during the past 30 days.

5. Have a habitual contact lens prescription that is current within the prior 6 months, and they must have worn that prescription for at least 2 weeks prior to entering the study.

 
Inclusion Criteria at Baseline Evaluation
 

6. The subject's vertex corrected spherical equivalent distance refraction must be in the range of -1.00 through -6.00 D in both eyes.

7. The subject's refractive cylinder must be 1.00 D or less.

8. The subject must have best corrected visual acuity of 20/25 or better in each eye.

----------------------------------	--

# **Clinical Study Protocol**

## **Johnson & Johnson Vision Care, Inc.**

Eligibility Criteria – Exclusion	
Potential subjects who meet any of the following criteria will be excluded from participating in the study:
 
Exclusion Criteria after Screening: The subject must not:
 

1. Be currently pregnant or lactating.

2. Have any ocular or systemic allergies or diseases that may interfere with contact lens wear.

3. Have any autoimmune disease or use of medication, which may interfere with contact lens wear. Habitual medications used by successful soft contact lens wearers are considered acceptable.

4. Have any previous, or planned, ocular or interocular surgery (e.g., radial keratotomy, PRK, LASIK, etc.).

5. Be currently wearing lenses in a monovision, multi-focal, toric, or extended wear modality.

6. Have participated in a contact lens or lens care product clinical trial within 14 days prior to study enrollment

7. Be an employee (e.g., Investigator, Coordinator, Technician) or immediate family member of an employee (including partner, child, parent, grandparent, grandchild or sibling of the employee or their spouse) of the clinical site.

8. Have a history of binocular vision abnormality or strabismus.

9. Have any infectious disease (e.g., hepatitis, tuberculosis) or contagious immunosuppressive diseases (e.g., HIV) by self-report.

 
Exclusion Criteria at Baseline Evaluation The subject must not:
 

10. Have any Grade 3 or greater slit lamp findings (e.g., edema, corneal neovascularization, corneal staining, tarsal abnormalities, conjunctival injection) on the FDA classification scale, any previous history or signs of a contact lens-related corneal inflammatory event (e.g., past peripheral ulcer or round peripheral scar), or any other ocular abnormality that may contraindicate contact lens wear.

11. Have any ocular infection.

12. Have any corneal distortion resulting from previous hard or rigid gas permeable contact lens wear.

----------------------------------	---

[figure not shown]
**Clinical Study Protocol**  
**Johnson & Johnson Vision Care, Inc.**

	13. Have entropion, ectropion, extrusions, chalazia, recurrent styes, glaucoma, history of recurrent corneal erosions, or aphakia.
Disallowed Medications/Interventions	Use of any prescription or over-the-counter (OTC) medications that may affect contact lens wear from 24 hours prior to receiving the study product through the study period of ~14 days. Habitual medications taken by successful soft contact lens wearers are generally considered acceptable. Note that habitual medications should be taken throughout the study period.  See section 9.1 for details regarding disallowed systemic medications.
Measurements and Procedures	LogMAR visual acuity, biomicroscopy, fit acceptance, GSI/MRD and CLUE questionnaire items.
Microbiology or Other Laboratory Testing	None.
Study Termination	The occurrence of an Unanticipated Adverse Device Effect (UADE) or Serious Adverse Event (SAE) for which a causal relationship to a test article cannot be ruled out, will result in stopping further dispensing investigational product. In the event of a UADE or SAE, the Sponsor Medical Monitor may unmask the treatment regimen of subject(s) and may discuss this with the Principal Investigator before any further subjects are enrolled.
Ancillary Supplies/ Study-Specific Materials	Preservative free rewetting drops/artificial tears or saline. ACUVUE™ RevitaLens will be used to transport any problematic lenses back to the Sponsor. logMAR visual acuity charts.
Principal Investigator(s) and Study Institution(s)/Site(s)	A full list of Principal Investigators, clinical sites, and institutions is kept separately from the Study Protocol and is included in the study Trial Master File.

# Clinical Study Protocol

## Johnson & Johnson Vision Care, Inc.

Figure 1: Study Flowchart

# Clinical Study Protocol

## Johnson & Johnson Vision Care, Inc.

### COMMONLY USED ABBREVIATIONS, ACRONYMS AND DEFINITIONS OF TERMS

ADE	Adverse Device Effect
ADHD	Attention Deficit Hyperactivity Disorder
AE	Adverse Event/Adverse Experience
BSCVA	Best Spectacle Corrected Visual Acuity
CFR	Code of Federal Regulations
CLUE	Contact Lens User Experience
COM	Clinical Operations Manager
COVID-19	Coronavirus Disease 2019
CRA	Clinical Research Associate
CRF	Case Report Form
CRO	Contract Research Organization
████████	████████
D	Diopter
DMC	Data Monitoring Committee
eCRF	Electronic Case Report Form
EDC	Electronic Data Capture
ETDRS	Early Treatment Diabetic Retinopathy Study
FDA	Food and Drug Administration
GCP	Good Clinical Practice
HEV	High Energy Visible light
HIPAA	Health Insurance Portability and Accountability Act
HIV	Human Immunodeficiency Virus
IB	Investigator's Brochure
ICH	International Council for Harmonization
IDE	Investigational Device Exemption
IEC	Independent Ethics Committee
IRB	Institutional Review Board
ISO	International Organization for Standardization
ITT	Intent-to-Treat
JJVC	Johnson & Johnson Vision Care, Inc.
LASIK	Laser-Assisted in Situ Keratomileusis
LogMAR	Logarithm of Minimal Angle of Resolution
OD	Right Eye
OS	Left Eye
OU	Both Eyes
PIG	Patient Instruction Guide
PQC	Product Quality Complaint
PRK	Photorefractive Keratectomy
PRO	Patient Reported Outcome
QA	Quality Assurance
SAE	Serious Adverse Event/Serious Adverse Experience
SAP	Statistical Analysis Plan
SAS	Statistical Analysis System

# Clinical Study Protocol

## Johnson & Johnson Vision Care, Inc.

SD	Standard Deviation
UADE	Unanticipated Adverse Device Effect
UV	Ultraviolet radiation
USADE	Unanticipated Serious Adverse Device Effect
VA	Visual Acuity

### 1. INTRODUCTION AND BACKGROUND

The range of high energy visible (HEV) light is roughly defined in the literature, with references stating 380-500 nm^5, 400-500 nm^6 and others stating 430-510 nm. This region of the electromagnetic spectrum has special meaning to the eye. It is light that we can see, but yet can have negative and positive effects on the eye. At the shorter wavelength end of the range, around 435±20 nm, the light has enough energy to cause premature damage to the retinal pigment epithelium and has been linked to macular degeneration. The shorter wavelengths are also scattered more than longer wavelengths (Rayleigh scattering), which create the blue sky and “blue haze” that we see when looking at distant objects. At the longer wavelength end of the range, around 480±20 nm, the light is responsible for regulating our circadian rhythms and pupillary light reflexes.

Ophthalmic devices that block the shorter HEV wavelengths while transmitting the longer wavelengths might experience an immediate visual improvement through better chromatic contrast, while benefitting in the long-term through enhanced retinal protection. This study will investigate the clinical performance of the prototype Test lenses against an otherwise similar Control.

#### 1.1. Name and Descriptions of Investigational Products

This study will evaluate a senofilcon A design prototype with new UV/HEV blocker against a commercially available marketed product ACUVUE OASYS® Brand Contact Lenses 1-Day with HydraLuxe™ Technology (AO1D). Further details about the test articles are found in section of this protocol. Note that the new UV/HEV blocker was previously identified as Theia I.

#### 1.2. Intended Use of Investigational Products

The intended use of the investigative product is for correcting myopia and for improving the visual experience by improving contrast. During the study, each test article will be worn bilaterally in daily wear, daily disposable modality for at least 6 hours per day and 5 days per week for approximately two weeks. The subject will wear both test articles in a cross-over study design.

#### 1.3. Summary of Findings from Nonclinical Studies

All previous pre-clinical findings were deemed satisfactory prior to proceeding with clinical trials on humans. For the most comprehensive nonclinical information regarding senofilcon A with new UV / HEV filter, refer to the latest version of the Investigator's Brochure.

# **Clinical Study Protocol**

## **Johnson & Johnson Vision Care, Inc.**

### **1.4. Summary of Known Risks and Benefits to Human Subjects**

The risks of wearing soft contact lenses are well known and are described in the Investigator's Brochure and Informed Consent. The material safety testing/lens release criteria was determined based on the Risk Assessment. Benefits to the subjects include the correction of their refractive error with the potential of improved contrast in HEV environments.

For the most comprehensive risk and benefit information regarding senofilcon A with new UV / HEV filter, refer to the latest version of the Investigator's Brochure.

## **2. STUDY OBJECTIVES, ENDPOINTS AND HYPOTHESES**

### **2.1. Objectives**

This study is being conducted to validate that the Test lens meets the customer requirements prior to launch. Senofilcon A with a new HEV / UV filter (Test) and without a new UV / HEV filter (Control) will be evaluated on several safety and efficacy measures.

# Clinical Study Protocol

## Johnson & Johnson Vision Care, Inc.

### Primary Objective(s)

The primary objective is to demonstrate that the Test lens meets all of the safety and efficacy requirements of the Design Validation Requirements as defined by [REDACTED]

### Secondary Objective(s)

The secondary objective is to demonstrate that the Test lens meets all of the Market Preferences as defined in [REDACTED]

## 2.2. Endpoints

**Primary Endpoint(s):** The following endpoints are defined in [REDACTED]

### Primary Safety Endpoints:

#### Biomicroscopy

Biomicroscopy (slit lamp findings) will be assessed for each subject eye across all study visits (including scheduled and unscheduled visits). FDA Slit Lamp Classification Scale will be used to grade the findings. The percentage of eyes with clinically significant slit lamp findings (i.e., Grade 3 or higher, or significant corneal infiltrates) will be analyzed.

#### Lens Fit Acceptance

Lens fitting will be assessed at dispensing and follow-up visits for each subject eye. The percentage of eyes with unacceptable lens fitting will be analyzed.

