#### Primary Hypotheses

##### Safety

1. The JJVCI investigational contact lens is non-inferior to the control lens with respect to the proportion of eyes with clinically significant slit lamp findings across all study visits. A non-inferiority margin of 5% will be used.
2. The JJVCI investigational contact lens is non-inferior to the control lens with respect to the proportion of eyes with unacceptable lens fitting at dispensing and follow up visit. A non-inferiority margin of 10% will be used.

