**Clinical Study Protocol**  
**Johnson & Johnson Vision Care, Inc.**

Visit 1: Treatment 1 Lens Fitting		
Step	Procedure	Details
1.22	General Lens Fit Assessment	
Evaluate lens centration, movement on blink, and push-up test for each eye.
 
An unacceptable fit is deemed by one of the following criteria:
 
 
• limbal exposure at primary gaze or with extreme eye movement.
 
• edge lift.
 
• excessive movement in primary and up gaze.
 
• insufficient movement in all three of the following conditions: primary gaze, up gaze, and push-up test.
 
 
Note: if lens fit is unacceptable for either eye, the subject will be discontinued from the study.

1.23	White Light Lens Surface Wettability	Record the white light lens wettability of both lenses.
1.24	Visual Acuity	Record the distance visual acuity with the contact lenses (OD, OS, and OU) to the nearest letter. Smaller lines must be shown until the subject incorrectly identifies at least 50% of the letters.
1.25	Continuance	
For the subject to continue in the study, they must meet all three of the following criteria:
 
 
• Visual acuity is 20/30 or better OD and OS.
 
• The lens fit is acceptable OD and OS.
 
• Investigator approval.
 
 
If the Investigator does not approve the dispensing of the first study lens, then the study is terminated for that subject.

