### 7.3. Unscheduled Visits

If, during the investigation, a subject requires an unscheduled visit to the clinical site, the following information will be collected, as appropriate:

- Chief complaint prompting the visit. If the reason is an adverse event, the applicable eCRF for the adverse event must be completed and subject record completed as appropriate.
- Date and time of the visit and all procedures completed at the unscheduled visit.
- Review of adverse event and concomitant medications.
- Documentation of any test article dispensed or collected from the subject, if applicable.
- Slit lamp findings (using the Slit Lamp Classification Scale).

If the Investigator withdraws a subject from the study, the final study visit case report forms must be completed indicating the reason(s) why the subject was withdrawn. The subject record must be completed documenting the date and primary reason for withdrawal and the study CRA notified.

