# Clinical Study Protocol

## Johnson & Johnson Vision Care, Inc.

Any ocular and non-ocular Adverse Events that are ongoing at the time of the study visit will be followed by the Investigator, within licensure, until they have resolved, returned to pre-treatment status, stabilized, or been satisfactorily explained. If further treatment i.e., beyond licensure is required, the subject will be referred to the appropriate health care provider.

The following information will be collected during an unscheduled visit.

Unscheduled Visit		
Step	Procedure	Details
U.1	Reason for unscheduled visit	Indicate if the only reason for the visit is that the subject requires additional test articles. If the reason is other than resupply of previously dispensed lenses, specify the reason for the visit.
U.2	Chief Complaints (if applicable)	Record the subject's chief complaints for reasons for the unscheduled visit.
U.3	Adverse Events and Concomitant Medications Review (if applicable)	Review any changes to the subject's medical history or concomitant medications from the previous study visit. Record any changes, and any adverse events.
U.4	Entrance VA (if applicable)	Record the entrance distance visual acuity (OD, OS) to the nearest letter.
U.5	Subjective Sphero-cylindrical Refraction (if applicable)	Perform bare-eye subjective sphero-cylindrical refraction with a phoropter (adopt the maximum plus to maximum visual acuity (MPMVA) approach and use the duo-chrome test for binocular balancing) and record the best corrected distance visual acuity to the nearest letter (OD, OS).
U.6	Slit Lamp Biomicroscopy (if applicable)	FDA Slit Lamp Classification Scale will be used to grade the findings. If the clearance of the fluorescein needs to be expedited, preservative-free rewetting drops may be instilled.  Limbal and Bulbar Conjunctival Hyperemia findings (████████) and Corneal Staining Assessment (████████) will be emphasized using a more detailed scale.  After the slit lamp examination, at the discretion of the Investigator, rinse the subject's eyes thoroughly with rewetting drops or saline.

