# **Clinical Study Protocol**

## **Johnson & Johnson Vision Care, Inc.**

- Subject not compliant with study lens wear schedule (i.e. wears study lenses less than at least 6 hours per day for at least 5 days a week over the 2 week wear period)
- Subject not successfully dispensed due to lack of efficacy and safety including poor vision, poor comfort or unacceptable fit.

For discontinued subjects, the Investigator will:

- Complete the current visit (scheduled or unscheduled).
- Complete the Final Evaluation, indicating the reason that the subject was discontinued from the study.
- Record the spherocylindrical refraction with best corrected distance visual acuity.
- Collect used test article(s) (worn or brought to the visit) from the subject and discard them, unless otherwise stated in section 7.2.
- Collect all unused test article(s) from the subject.
- Make arrangements for subject care, if needed, due to their study participation

Additional subjects will be enrolled if a subject discontinues from the study prematurely.

In cases where a subject is lost to follow-up, every possible effort must be made to contact the subject and determine the reason for discontinuation/withdrawal. The measures taken to follow up must be documented including two written attempts and a certified letter (or equivalent) as the final attempt.

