### The Model:

Let  $Y_1$  and  $Y_2$  denote the binary outcomes of lens fit acceptance (Yes/No) in left and right eyes, respectively, across dispensing and follow-up visits when wearing a study lens. Considering the correlation,  $\rho$ , between  $Y_1$  and  $Y_2$ , the distribution of the sum  $Y = Y_1 + Y_2$  is obtained by the mixture of two variables. One of them follow a binomial distribution  $Bin(2, p)$  with mixing probability  $(1 - \rho)$  and the other one follows a modified Bernoulli distribution,  $MBern(p)$ , taking value 0 and 2 rather than conventional 0 and 1, with mixing probability  $\rho$ :

$$P(Y = y | p, \rho) = (1 - \rho)Bin(2, p)I_{A1} + \rho MBern(p)I_{A2},$$

where  $I_{A1} = \{0, 1, 2\}$ ,  $I_{A2} = \{0, 2\}$  and  $p$  is the probability of success (i.e., acceptable lens fitting).

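### Lens fit that becomes unacceptable during wear and leads to exit before Visit 2 has no assessment step and falls outside the lens-fit primary endpoint

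*Combined protocol and SAP*

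**What the plan says.** The endpoint (section 2.2) is confined to two occasions: "Lens fitting will be assessed at dispensing and follow-up visits for each subject eye". The hypothesis (section 2.3) concerns the "proportion of eyes with unacceptable lens fitting at dispensing and follow up visit", with a 10% margin, and the model (section 14.5) takes each eye's outcome "across dispensing and follow-up visits when wearing a study lens". Section 2.3 requires every primary hypothesis to be met. By contrast, biomicroscopy is assessed "across all study visits (including scheduled and unscheduled visits".

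To be dispensed, a subject must satisfy step 1.25: "The lens fit is acceptable OD and OS". Fit is next judged at Visit 2, step 2.9.

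For visits in between, section 7.3 says "The following information will be collected during an unscheduled visit" and lists U.1 to U.8: reason, complaints, adverse events and medications, acuity, refraction, slit lamp, dispensing and exit acuity. For a discontinued subject, section 8.2 asks the investigator to "Complete the current visit (scheduled or unscheduled" and then the Final Evaluation. Steps F.1 to F.4 cover disposition and reason, keratometry, refraction and slit lamp. Neither list includes lens fit.

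The safety population (section 14.3) needs only one recorded observation. Section 14.9 imputes nothing, and its multiple-imputation option covers only the primary efficacy analyses.

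**The concern.** Every dispensed subject already has an acceptable fit on record, and step 1.18 lets that be made after as little as five minutes of settling. Fit that deteriorates with wear can enter the endpoint only at step 2.9. A subject whose lens becomes tight, loose or edge-lifting and who leaves before Visit 2 never reaches that step. Whether the outcome is observed then depends on the outcome itself: the failures troublesome enough to end participation are the ones the endpoint can miss. Because this is a non-inferiority comparison, losing events can make a real difference look smaller. An analysis plan written later cannot recover an assessment that was never made.

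**Working it through.** **1. The plan's own figure.** Inputs from section 14.2: unacceptable-fit rate 5% in both arms, between-eye correlation 0.70, margin 10%, 95% interval, 140 subjects (taken as 70 per arm), stated power 83%.

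SE = √[(pT(1−pT) + pC(1−pC)) × (1+0.7)/(2n)] = √[(0.0475 + 0.0475) × 1.7/140] = 0.0340.

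Power = Φ(0.10/0.0340 − 1.96) = Φ(0.984) = 83.8%.

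Simulating 2,000 trials from the section 14.5 mixture model with its stated priors (evaluated on a grid rather than by MCMC) gives 85.0%. The stated figure is sound. At the planned size, power with both rates at 5% is about 98% (143 per arm) to 99% (160 per arm).

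**2. Direction of the bias.** Let fT and fC be the shares of failing subjects whose failure goes unrecorded. Then:

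recorded difference = (1−fT)pT − (1−fC)pC = (pT−pC) − (fT·pT − fC·pC).

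It moves towards non-inferiority when fT·pT exceeds fC·pC. With equal shares f it becomes (1−f)(pT−pC), so a real excess on Test shrinks even without differential loss. If the true rates are equal, equal loss leaves the difference at zero.

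**3. Effect on false non-inferiority.** The documents give no rate of between-visit fit failure, so f is assumed over a range. True rates are set at the margin (Test 15%, Control 5%), correlation 0.7, 143 per arm, 1,000 simulated trials per cell (simulation error about 1 to 2 points). A lost failure removes both eyes' events.

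| Share lost | Same in both arms | Test only | Control only |
|---|---|---|---|
| 0 | about 3–4% | about 3–4% | about 3–4% |
| 10% | 8% | 10% | 2.4% |
| 25% | 20% | 28% | 1.5% |
| 50% | 61% | 84% | 0.8% |

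At 160 per arm the equal-loss column reads 7%, 21% and 67%.

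**4. How many failures would change the conclusion.** Under the same model, with no failures in Control, the upper 97.5% posterior limit first reaches 0.10 at 9 bilateral Test failures of 143, or 11 of 160.

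**5. Stress case.** Suppose k of 160 Test subjects are lost for bilateral fit failure and none in Control, true rates 15% and 5%, normal approximation.

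- k = 4: Test recorded at 0.15 − 4/160 = 0.125, difference 0.075, SE = √[(0.1094 + 0.0475) × 1.7/320] = 0.0289. Φ(0.025/0.0289 − 1.96) = 13.7%.
- k = 8: Test recorded at 0.10, difference 0.05, SE 0.0270. Φ(0.05/0.0270 − 1.96) = 45.6%.
- k = 0: 2.5%.

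**6. Does coding rescue it?** In the k = 8 case, 24 of 160 Test subjects truly fail (15%) and 16 are recorded. Counting the eight as acceptable gives 16/160 = 10.0%. Dropping them gives 16/152 = 10.5%. Either way the failures are lost.

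**The case against.** Four stronger readings are tempting, and the documents support none of them.

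- *A reader might infer that the plan counts such a subject as an acceptable fit.* No section says so. It follows from the dispensing record plus no imputation, and section 14.1 defers detail to a stand-alone SAP that is not part of the supplied document. What stands is that the coding of an eye with only a dispensing record is undefined for a primary endpoint.
- *A reader might infer that the failure cannot be recorded at all.* Section 7.3 asks for the "Date and time of the visit and all procedures completed at the unscheduled visit", U.1 and U.2 capture the reason and complaint, and F.1 captures the reason for leaving. Section 14.1 excludes unscheduled visits from efficacy only. A trace is therefore likely, but no fit check is required and nothing brings the trace into the endpoint. The only fit-related reason listed in section 8.2 concerns subjects not successfully dispensed, whom step 1.22 already covers.
- *A reader might infer that non-inferiority is always favoured.* The forms are the same in both arms, and loss confined to Control makes non-inferiority harder to declare.
- *A reader might take 14% and 46% as expected error rates.* They assume loss in Test only and a Test rate three times the 5% that section 14.2 calls its worst case; k = 8 is one third of all Test failures (8/24). Nor is the planned shortfall of 34 (320 − 286, or 17 per arm) all post-dispensing loss. Section 4.3 counts enrolment from consent, Table 1 gives 143 to 160 randomized per arm, and fit failures at Visit 1 are already counted.

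It is also fair that section 14.2 reports no unacceptable fit on either lens historically, and that Table 3 gives both lenses the same material, base curve, diameter, modulus and centre thickness. A fit difference is not expected. Subjects who continue are reassessed at step 2.9.

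**Conclusion.** The gap is real but narrow: an unacceptable fit that arises after dispensing and ends in exit before Visit 2 has no required assessment and lies outside the endpoint as defined, unlike a slit lamp finding at the same visit. On a plain reading that failure is lost.

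Loss at equal rates in both arms, or heavier in Test, pulls a true Test excess towards non-inferiority; loss mainly in Control does the opposite. The size cannot be estimated from the documents and is probably small, given the absence of historical fit failures, the identical nominal geometry, and the 9 to 11 bilateral Test failures against none in Control needed to change the conclusion. The table in the working shows what would happen at the margin under assumed loss shares; it is not a forecast. The case for acting is that the endpoint must be passed, the missingness depends on the outcome, and the remedy is cheap.

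**What to change.** 1. Add the step 2.9 fit assessment, when the subject arrives wearing the study lenses, to unscheduled visits not solely for resupply and to the Final Evaluation for early exits.
2. In sections 2.2, 2.3 and 14.5, define the endpoint as any unacceptable fit at dispensing, follow-up, unscheduled or early-exit visits, in line with biomicroscopy.
3. State how an eye with only a dispensing record is coded.
4. Add a sensitivity analysis that counts post-dispensing exits attributed to fit as events, using the reason recorded at F.1.

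The cost is a few minutes at a few visits with the slit lamp and staff already there, one added eCRF item, a minor amendment and matching SAP wording. The observed unacceptable-fit rate may be slightly less favourable.
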